19.0 APPENDIX C: Image guided hip injection technique

[figure not shown]
Intra-articular injections into the hip joint will be administered under fluoroscopic or ultrasound guidance using standard techniques, such as currently used for intra-articular injection of corticosteroids. *Sterile drapes or other suitable means should be used to block the patient's view of the injection procedure and the imaging monitor.* The target injection site is the femoral neck, just below the femoral head and inside the joint capsule. The specific approach angle for the injection will be at the discretion of the injecting Investigator. A typical injection procedure is as follows:

The patient is placed in the supine position with the target hip rotated internally 15-20°. The patient should be draped with only the injection site exposed. The skin at the injection site should be prepped using a 1% betadine solution. The soft tissues around the injection site may be anesthetized prior to IA injection using a local injection (e.g. lidocaine) or a topical refrigerant anesthetic (e.g. ethyl chloride). Under guidance, an 18-20 gauge needle will be inserted anteriorly towards the anterior-inferior joint capsule, approximately 8-10 cm below the inguinal ligament and just below the femoral head, taking care to avoid the femoral artery. Needle placement in the capsule is illustrated in Figures 1 and 2. ***Extension tubing that connects the needle to the syringe should not be used.*** If using fluoroscopic guidance, a small amount of fluoroscopic contrast agent (0.5 to 1.0 ml) should be injected through the needle to verify intra-articular placement. If using ultrasound guidance, a small volume of air (up to 0.5 ml) may be injected to verify IA positioning. If pooling of the contrast agent or air around the needle tip is observed, the needle should be repositioned. When contrast agent or air is successfully injected into the joint, intra-articular placement is confirmed.

Figure 1: Injection technique for hip, shown here using ultrasound guidance to inject the left hip (12).

Figure 2: Target needle placement at the femoral neck, shown with and without ligamentous anatomy.

Following confirmation of intra-articular needle placement, the joint may be aspirated to remove osteoarthritic synovial fluid. Finally, 4 ml of either MONOVISC or saline should be injected into the joint. *Intra-articular* anesthetic should NOT be administered as part of the injection procedure.

Following the injection, the patient should be advised to maintain a low level of physical activity for the next 24 hours. Cold therapy and/or acetaminophen may be prescribed to address short term injection site pain.

	Radiographs are not collected post-baseline and will therefore not be summarized.....	24
13.5.3	Study Specific Data.....	24
13.6	Site Heterogeneity.....	24
13.7	Poolability Analysis	24
13.8	Additional Analyses.....	24
14	PLANS FOR INTERIM ANALYSIS (IA)	27
14.1	The Objectives of the IA.....	27
14.2	Efficacy and Safety Variables	27
14.3	Timing and Frequency of the IAs	27
14.4	Analysis sets for the IA.....	27
14.5	Data cut criteria	27
14.6	Analysis Plan	28
14.7	Possible Decisions or Actions Based on the IA Results	28
14.8	Statistical Approach for Modifying the Study Design	28
15	LIST OF TABLES, FIGURES, AND SUBJECT DATA LISTINGS.....	28
16	REFERENCES.....	28

1 List of Abbreviations

AE	Adverse Event
AT	As Treated
BSDM	Biostatistics and Data Management
CSP	Clinical Study Protocol
IA	Interim Analysis
IDE	Investigational Device Exemption
ITT	Intent-to-Treat
H_A	Alternative Hypothesis
H_0	Null Hypothesis
N/A	Not Applicable
NRS	Numerical Rating Scale
MITT	Modified Intent to Treat
OA	Osteoarthritis
PGA	Patient Global Assessment
PP	Per-Protocol
SAP	Statistical Analysis Plan
WOMAC	Western Ontario and McMaster Osteoarthritis Index

2 Modifications in Analysis from the Clinical Study Protocol

The basis of this SAP is the Clinical Study Protocol (CSP). For reasons of clarity certain redundant text has been omitted and changes have been made to address any typographical errors and improve consistency of terminology. In addition, substantive changes are presented in Table 1, below.

Table 1 Summary of Substantive Changes

Content	Modification	Justification
Block Randomization, stratified by study site	One Master Randomization List was created with which to sequentially label patient kits as MONOVISC or saline.	Stratification of randomization by study site was not feasible because it would have required a significant quantity of additional product, storage of randomized product by site, and added complexity in procedures with the supply vendor.
Mean Change from Baseline through 26 Weeks in WOMAC A1	Added endpoint and method of analysis	In addition to assessing the primary endpoint, WOMAC A1 walking pain

Content	Modification	Justification
		score change from baseline at 26 weeks, interest lies in assessing the difference in the mean change from baseline in WOMAC A1 over the entire study period.
Interim Analysis	An unblinded analysis team (separate and firewalled from the study team) will be responsible for the conduct of the Interim Analysis rather than a member of the Strategic Medical Affairs department	As the analysis will be used to make a go/no go decision on study conduct, a rigorous approach to the analysis is warranted.

3 The Study Objectives

The primary objective of this study is determine whether two intra-articular injections of MONOVISC, separated by 1 month, are superior to two intra-articular injections of physiologic saline, separated by 1 month, in relieving hip osteoarthritis pain, as determined by reduction in walking pain change from baseline.

We hypothesize that two (2) monthly injections of MONOVISC will be an effective treatment regimen for hip OA patients.

4 Study Design

This study is a prospective, multi-center, double-blinded, randomized, controlled, superiority study comparing intra-articular injections of MONOVISC High Molecular Weight Hyaluronan with intra-articular injections of physiologic saline. The study will take place in the United States, with up to 25 investigational sites. Subjects will be randomized through a 2:1 schema to receive either two (2) injections of 4 ml of MONOVISC, separated by 1 month (active treatment), or two (2) monthly injections of 4 ml of saline, separated by 1 month (control treatment).

Subjects will return for follow-up visits at 2, 4, 8, 16, and 26 weeks after the first injection.

The primary endpoint will be pain during walking (WOMAC A1) change from baseline at the 26 week time point.

An interim analysis (IA) of the primary endpoint will be conducted after 74 MONOVISC and 37 saline subjects have received both injections of MONOVISC or saline and completed their per protocol 26 week follow up visit. A stopping rule for futility will be implemented, such that the study will be terminated if the improvement of MONOVISC over saline (change from baseline) is less than 0.4 on a 10 point Numerical Rating Scale (NRS) in both the Per Protocol Analysis Set for the 26 week interval and the As Treated Analysis Set for the 26 Week interval. If the improvement of MONOVISC over saline (change from baseline) is more than 0.4 NRS in either of these analysis sets, the study will continue to completion. Details of planned analyses are provided in Section 14.

5 Treatment Assignment

The treatment groups in this study are:

MONOVISC: Two intra-articular injections of MONOVISC High Molecular Weight Hyaluronan, separated by 1 month (active treatment).

Saline: Two injections of 4 ml saline, separated by 1 month (control treatment).

5.1 Randomization

Subjects will be randomized in a 2:1 ratio to receive either treatment with MONOVISC or treatment with Saline. Block randomization (random blocks of size 3 or 6) will be used to create a Master Randomization List and patient kits of MONOVISC and saline will be sequentially numbered according to this list. With this randomization scheme, each study subject will be associated with a unique kit number, and the order of randomized subjects at each investigational site will be distinct. Prior to initiation of the study, investigational sites will be provided with an initial, sequentially numbered quantity of kits to be used, and as these kits are utilized, additional quantities of sequentially numbered kits can be ordered as needed through an electronic re-order system. The kit will not contain any labeling to indicate whether the patient is receiving MONOVISC or Saline. After the first injection, the remaining syringe will be returned to the storage site for the second injection.

5.2 Blinding

All clinical research and biostatistics personnel at DePuy Synthes Mitek Sports Medicine will remain blinded to treatment assignment until the end of the study with 2 exceptions:

- an employee within DePuy Synthes Mitek Sports Medicine Strategic Medical Affairs will be designated to maintain the Master Randomization, to facilitate any medical safety reviews, if necessary, and to facilitate the planned interim futility analysis.
 - [name], Franchise Medical Director, DePuy Synthes is currently fulfilling this role. If a change is required, a replacement for this responsibility will be assigned and documented in a note to file.
- A team of qualified employees from within DePuy Synthes Mitek Sports Medicine Biostatistics and Data Management (BSDM) department who will be designated to conduct the Interim Analysis. Members of this team will not be otherwise associated with the conduct of the study.

6 Levels of Significance

In general, confidence intervals will be 2-sided, 95% confidence intervals, and p-values will also be 2-sided; p-values below 0.05 will be deemed to be statistically significant.

[figure not shown]
6.1 Control of Type 1 Error

Family-wise control of Type I Error across all primary and secondary endpoints will be accomplished using the following gatekeeping strategy which is depicted in Figure 1.

If the study is successful and the primary endpoint analysis demonstrates a statistically significant difference (favoring MONOVISC vs. Saline) at 26 Weeks, then we will test the WOMAC A1 change from baseline at 16 Weeks for a significant difference (favoring MONOVISC vs. Saline). If this is successful, we will test the difference at 8 Weeks; if this is successful, we will test the difference at 4 Weeks; and if this is successful, we will test the difference at 2 Weeks. At any point, if one of these comparisons fails to be statistically significant, then we will cease further testing in the specified order. Each of these tests will be conducted utilizing the primary endpoint analysis on the Modified Intent to Treat Analysis Set for Longitudinal Analysis. We will test each of the secondary endpoints with a 2-sided p-value against threshold of 0.05 (a 2-sided 5% alpha) with no further adjustment for multiplicity.

Further detail of the hypotheses tested is found in Section 10.

Figure 1 Primary and Secondary Gatekeeping Procedural Flow

Note: The hypothesis tests indicated above are to be performed on the endpoints which we have specified as primary and secondary, WOMAC A1 change from baseline at 26 (primary) weeks and also at 2, 4, 8, and 16 weeks.

7 Interval Windows

The study windows are presented in the Time and Events Schedule (CSP Section 1.1).

For analysis purposes, the baseline/screening evaluation is to be done within 30 days prior to the first injection; the first injection is considered to be day 0. The 2, 4, 8, 16 and 26 Week visits will occur in the time intervals (days) indicated in Table 2, below.

Table 2 Study Interval Windows

Analysis Visit Label	Nominal Study Visit	Study Interval
Baseline	Baseline/Screening	-30 to 0
2 Week	Day 14 ± 7 days	11 to 17
4 Week	Day 28 ± 7 days	21 to 35
8 Week	Day 60 ± 14 days	46 to 74
16 Week	Day 120 ± 14 days	105 to 134
26 Week	Day 180 ± 14 days	159 to 201

Note:

Day 0 is defined as the Study Day of first injection.

Baseline is defined as the last non-missing assessment prior to first injection.

Baseline must occur no more than 30 days after Screening.

8 Handling of Missing Data

The primary efficacy endpoint analysis will be conducted on the MITT Analysis Set, which consists of all primary endpoint data on all As Treated (AT) subjects (regardless of whether or not there were protocol deviations associated with the data) for the 2, 4, 8, 16 and 26 week visits. In this MITT Analysis Set, missing primary endpoint data for the 26 Week visit will be imputed with multiple imputation methodology using SAS PROC MI with the regression method and a monotone missing data pattern.

No imputation of missing data will be performed for visits other than the 26 Week visit.

9 Primary and Secondary Endpoints

The primary and secondary endpoints are derived from the Western Ontario and McMaster Universities Arthritis Index (WOMAC), which is widely used in the evaluation of Hip and Knee Osteoarthritis. The WOMAC is available in over 65 languages and has been linguistically validated. It is a self-administered questionnaire consisting of 24 items divided into 3 subscales, A, B, and C: A) Pain (5 items), B) Stiffness (2 items), and C) Physical Function (17 items). The overall WOMAC score is determined by summing the scores across the 3 subscales and the score ranges include 0–24 (derived from the NRS scale). Higher scores on

the WOMAC indicate worse pain, stiffness, and functional limitations. Specific scoring details will be provided in the table shells document referenced in Section 15.

The WOMAC A is the pain subscale of the WOMAC questionnaire. Again, response options for individual questions are 0 through 10, where 0 indicates no pain and 10 indicates worst possible pain. The WOMAC A pain subscale scores ranges are 0-50 NRS.

WOMAC A1 is the first question of the WOMAC A and specifically addresses pain during walking. Response options are 0 through 10 NRS, where 0 indicates no pain and 10 indicates worst possible pain.

9.1 Primary Endpoint

The primary efficacy endpoint in this study is the WOMAC A1 walking pain score change from baseline at 26 weeks.

9.2 Secondary Endpoints

The secondary endpoints in this study are also based on the WOMAC A1 walking pain score change from baseline; four secondary endpoints are defined, one for each of the remaining post-baseline time points: at the 2, 4, 8, and 16 Week time points. Analysis will be conducted using the MITT Longitudinal Analysis Set and will include data from weeks 2 through 26 weeks. However, no imputation will be done for any time point other than the 26 Week.

9.3 Tertiary Endpoints

The following are considered tertiary endpoints, and will be summarized in tables of summary statistics:

Walking Pain:

WOMAC A1 score mean change over 26 Weeks.WOMAC A1 score at the 2, 4, 8, 16 and 26 Week time points.

WOMAC A1 score change from baseline area under the curve (AUC).

Pain:

WOMAC A score at the 2, 4, 8, 16 and 26 Week time points.

WOMAC A score change (improvement) from baseline at the 2, 4, 8, 16 and 26 Week time points.

Pain, Stiffness and Physical Functioning:

Total WOMAC score at the 2, 4, 8, 16 and 26 Week time points.

Total WOMAC score change (improvement) from baseline at the 2, 4, 8, 16 and 26 Week time points.

OMERACT-OARSI Responder Rate:

The OMERACT-OARSI responder rate will be derived from the WOMAC A (Pain) and C (Function) subscale scores and PGA score, as discussed in Pham (2003)¹.

Response will be determined at each visit and with the available data (no imputation of missing data will be performed to assess response). To be considered a Responder at a visit either criteria 1 or 2 must be met:

1. WOMAC A (Pain) or WOMAC C (Function) relative change from baseline $\geq 50\%$ and an absolute change ≥ 20
2. Improvement in at least 2 of the following:
 - WOMAC A (Pain) Score: a relative change from baseline $\geq 20\%$ and an absolute change from baseline ≥ 10 .
 - WOMAC C (Function) Score: a relative change from baseline $\geq 20\%$ and an absolute change from baseline ≥ 10 .
 - Patient's global assessment (PGA): a relative change from baseline $\geq 20\%$ and absolute change from baseline ≥ 10 .

In 1 and 2 above, relative change will be calculated as:

$100\% \times \frac{\text{Score at Visit} - \text{Baseline Score}}{\text{Baseline Score}}$ and absolute change will be calculated as:

Score at Visit – Baseline Score.

Disease Activity:

Patient Global Assessment (PGA) at the 2, 4, 8, 16, and 26 Week time points.

Health Outcomes:

Physical and Mental Composite scores of the SF-12 outcomes at study defined time-points

Rescue Medicine Consumption:

Acetaminophen use from baseline through 26 Weeks.

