17.0 APPENDIX A: Definitions

PATIENT REPORTED OUTCOME CASE REPORT FORMS

NRS: Numerical Rating Scale. The patient reports an integer pain score between 0 and 10, with 1 being no pain and 10 being worst pain imaginable.

SF-12: The Short Form-12 was designed to measure general health status from the patient's point of view. The SF-12 is a multi-purpose, short-form health survey with only 12 questions. It yields an 8-scale profile of functional health and well-being scores as well as psychometrically-based physical and mental health summary measures and a preference-based health utility index. It is a generic measure, as opposed to one that targets a specific age, disease, or treatment group. Accordingly, the SF-12 has proven useful in surveys of general and specific populations, comparing the relative burden of diseases, and in differentiating the health benefits produced by a wide range of different treatments.

WOMAC: The Western Ontario and McMaster Universities Arthritis Index (WOMAC) was developed in 1982 at Western Ontario and McMaster Universities and is widely used in the evaluation of Hip and Knee Osteoarthritis. The WOMAC is available in over 65 languages and has been linguistically validated. It is a self-administered questionnaire consisting of 24 items divided into 3 subscales: pain (5 items), stiffness (2 items) and physical function (17 items). The WOMAC takes approximately 12 minutes to complete. Higher scores on the WOMAC indicate worse pain, stiffness, and functional limitations.

WOMAC A: The pain subscale of the WOMAC questionnaire

WOMAC A1: The first question of the WOMAC A questionnaire that addresses pain during walking.

PROTOCOL DEVIATION

A protocol deviation is defined as an incident where the Investigator or site personnel did not conduct the study according to the investigational plan, protocol or the Investigator agreement.

Any deviation from patient inclusion and exclusion criteria or patient informed consent procedures, or any deviation from a protocol requirement such as incomplete/inadequate patient testing procedures, follow-ups performed outside specified time windows, etc.

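### As printed, the OMERACT-OARSI responder rule in SAP 9.3 counts WOMAC worsening as response, contradicts its own word for improvement, and leaves the PGA limb unreachable

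*SAP*

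**What the plan says.** SAP 9.3 (Tertiary Endpoints) derives the responder rate from WOMAC A, WOMAC C and the PGA. A patient responds at a visit by meeting either of two criteria.

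- Criterion 1: "WOMAC A (Pain) or WOMAC C (Function) relative change from baseline" of at least 50%, together with an absolute change of at least 20.
- Criterion 2: "Improvement in at least 2 of the following". The list is WOMAC A, WOMAC C and the PGA, each needing a relative change of at least 20% and an absolute change of at least 10. The PGA entry reads "global assessment (PGA): a relative change from baseline", with the same two thresholds as the WOMAC entries.

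The formulas follow, introduced by "In 1 and 2 above, relative change will be calculated as". Relative change is 100% × (score at visit − baseline) / baseline. Absolute change is score at visit − baseline.

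Direction and range are given elsewhere. Protocol Appendix A states "Higher scores on the WOMAC indicate worse pain, stiffness, and functional limitations", and SAP Section 9 says the same. SAP Section 9 scores items 0 to 10 and adds "The WOMAC A pain subscale scores ranges are 0-50 NRS". Protocol Appendix A lists "pain (5 items), stiffness (2 items) and physical function (17 items"). SAP 13.8 tabulates the PGA in ordinal categories 0 through 10. Neither document states which end of the PGA is good.

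SAP Sections 9 and 15 leave further scoring detail to a table-shells document due before final database lock.

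**The concern.** Two separate faults sit in the same few lines.

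**Sign.** A fall in WOMAC is an improvement, so visit minus baseline is negative for a patient who gets better. The thresholds are positive. Criterion 1 has no direction word, so read literally it selects patients who got worse. Criterion 2 does have one, and it conflicts with formulas that the SAP expressly applies to both criteria.

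**Scale.** The same absolute cut-offs are applied to instruments with very different ranges, and no rescaling is stated. A 10-point change on a 0 to 10 PGA is the whole scale.

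At stake is whether this endpoint, named in the protocol and reported at five visits, measures response at all. SAP 13.8 plans counts and proportions for it. SAP Section 13 also provides Fisher's exact p-values for dichotomous variables generally, so a between-group comparison may be reported too.

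**Working it through.** The plan gives no figure to reproduce here, because the point concerns the logic of a derivation. It can be checked by listing every possible pair of scores.

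**Inputs**
- WOMAC A: 0–50 (SAP Section 9).
- WOMAC C: 17 items × 10 = 0–170. This is derived from the item count; the range itself is not printed.
- PGA: 0–10 (SAP 13.8).
- Thresholds and formulas: SAP 9.3.

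**Step 1: sign.** Take all integer (baseline, visit) pairs with baseline ≥ 1, since relative change is undefined at 0. Apply the printed formulas, then reverse the sign.

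| Limb | Pairs meeting it as printed | Direction | Pairs with sign reversed | Direction |
|---|---|---|---|---|
| Criterion 1, WOMAC A | 465 | all worse | 466 | all better |
| Criterion 1, WOMAC C | 9,253 | all worse | 7,186 | all better |
| Criterion 2, WOMAC A | 820 | all worse | 861 | all better |
| Criterion 2, WOMAC C | 11,816 | all worse | 11,541 | all better |
| Criterion 2, PGA | 0 | – | 1 (10 to 0) | fall |

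For example, WOMAC A falling from 30 to 10 gives (10 − 30)/30 = −66.7% and −20: not a responder. Rising from 30 to 50 gives +66.7% and +20: a responder. As printed, WOMAC A cannot meet criterion 1 from any baseline above 50 − 20 = 30. In criterion 2, no WOMAC pair satisfies both the formula and the word improvement.

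**Step 2: the PGA limb.** There are 11 × 11 = 121 pairs on 0–10. As printed, a change of at least 10 occurs only for 0 to 10, where relative change divides by zero, so none qualifies. This is true whichever way the PGA is scored. With the sign reversed, only 10 to 0 qualifies. Either way, two of three in effect means both pain and function.

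**Step 3: cut-offs as a share of range.**

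| Component | 20 points | 10 points |
|---|---|---|
| WOMAC A | 20/50 = 40% | 10/50 = 20% |
| WOMAC C | 20/170 = 11.8% | 10/170 = 5.9% |
| PGA | not used | 10/10 = 100% |

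**Step 4: what remains after correcting only the sign.** Criterion 1 then needs a fall of max(20, 0.5 × baseline). The 20-point cut-off overrides the 50% rule when baseline is below 40, which is 40/50 = 80% of the WOMAC A range but 40/170 = 23.5% of the WOMAC C range. Criterion 2 needs max(10, 0.2 × baseline). On WOMAC A the 20% rule never binds, because 20% of the maximum, 50, is already 10.

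Compare two baselines at 60% of range. At WOMAC A = 30, criterion 1 needs 20/30 = 67% and criterion 2 needs 10/30 = 33%. At WOMAC C = 102, they need 50% and 20%. Pain must improve by a larger fraction than function to count, with no stated reason.

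**Illustration only.** None of these inputs comes from the documents. Assume each component, on a 0–10 equivalent, has baseline mean 5.8 (SD 1.5) and mean change −2.1 (SD 2.0), with correlation 0.7 among components and a higher PGA being worse. The simulated responder rate is then:

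| Reading | Central case | Range over 108 scenarios |
|---|---|---|
| As printed throughout | 1.7% | 0.5–13% |
| Criterion 1 as printed, criterion 2 as improvement | 48% | 24–63% |
| Both as improvement, raw scores | 54% | 29–70% |
| Both as improvement, assumed 0–100 scale | 71% | 44–86% |

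The scenarios vary baseline mean (5.0 to 6.5), mean change (−1.0 to −2.7), SD of change (2.0 to 2.5) and correlation (0.5 to 0.85).

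**The case against.** The strongest reply is that the intent is obvious. The endpoint is a responder rate, criterion 2 speaks of improvement, and 9.3 glosses change as improvement for WOMAC A and the WOMAC total. A competent programmer would reverse the sign. That stands as far as it goes: this is a specification error, not evidence that the analysis will be run backwards. It does not settle the scale, the PGA direction or a zero baseline.

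Second, scoring detail is deferred to the shells document, which may correct all of this, and the rule is tied to a cited publication. Neither removes the conflict. The SAP prints its own formulas and cut-offs, and adding detail is different from reversing a printed formula. Protocol 11.0 also requires deviations from the final SAP to be noted in the final report.

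Third, nothing in the documents says the cut-offs belong on a 0–100 scale. That is correct, and it is treated here as an assumption.

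Fourth, the simulation rests on invented inputs and compares no treatment arms, so it shows no effect on a between-group conclusion. That is also correct; the case rests on the enumeration.

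Fifth, a zero baseline is unlikely, at least for WOMAC A, because entry requires walking pain of 4 to 8. That is fair, but the rule still needs a line.

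Finally, SAP Section 9 says of the overall WOMAC that "the score ranges include 0–24 (derived from the NRS scale"), although 24 items of 0–10 sum to 240. This needs correcting, but the responder rule does not use the total, so it is a side issue.

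**Conclusion.** The concern holds. Followed literally, SAP 9.3 classifies only worsening as meeting criterion 1, gives criterion 2 two incompatible readings, and removes the PGA from a rule said to be derived from it. The sign and PGA results are exact and need no distributional assumption. The WOMAC C counts and percentages rest on the derived 0–170 range, but the sign finding does not. Reversing the sign alone is insufficient: the PGA limb would still be met by only one pair of scores in 121.

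The consequence is limited to one tertiary endpoint outside the gatekeeping sequence of SAP 6.1. The primary and secondary analyses and the interim futility decision are unaffected. It should be corrected, because the printed rule gives a wrong responder rate and the plausible repairs do not agree with one another.

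**What to change.** Amend SAP 9.3 itself, rather than leaving the correction to the shells document:

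1. Define improvement in WOMAC A and C as baseline minus score at visit, and relative improvement as 100% × that difference / baseline. Use the word improvement in both criteria.
2. State which end of the PGA is worse and sign its change to match.
3. Either put all three components on one stated common scale before applying the 20- and 10-point cut-offs, or give equivalent cut-offs for each scale. A 0–100 scale is the assumed intent; the sponsor should confirm this against the responder criteria it cites.
4. State how relative change is handled when baseline is 0.

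Correct the overall WOMAC range in SAP Section 9 at the same time. The cost is a few lines of SAP text and derivation code. No new data are needed, since the WOMAC and PGA are already collected at every visit from baseline onward.
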